13.1. Efficacy Analysis

13.1.1. Analysis Populations

The following subject populations will be evaluated and used for presentation and analysis of the data:

- The Randomized Population will include all randomized subjects.
- The Intent-to-Treat (ITT) Population will include all randomized subjects who receive any amount of investigational product (OCA or placebo). The ITT Population will be the primary population used for efficacy analyses. Treatment assignment will be based on the randomized treatment.
- The Safety Population will include all subjects who received any amount of investigational product (placebo or OCA). The Safety Population will be the primary population used for safety analyses. Treatment assignment will be based on the treatment actually received.
- The PK population will include all OCA subjects who have at least one confirmed fasted analyzable sample. Subjects must have been fasting for approximately 8 hours prior to the visit and must not have any major protocol deviations that potentially affect exposure levels. The PK population will be used for OCA PK analyses.
- The Overall Historical Control Population will include subjects from the United Kingdom (UK) -PBC Group and Global PBC Study Group databases with demonstrated comparability to randomized subjects in this clinical study (747-302) with respect to both subject characteristics and disease progression.
- The UK-PBC Historical Control Population will include subjects from the UK-PBC Group databases with demonstrated comparability to randomized subjects in this clinical study (747-302) with respect to both subject characteristics and disease progression.
- The Global PBC Historical Control Population will include subjects from the Global PBC Study Group database with demonstrated comparability to randomized subjects in this clinical study (747-302) with respect to both subject characteristics and disease progression.

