- Review and record prior concomitant medications.
- Review and record any non-study related medical or surgical treatment procedures and any medically relevant health care professional (HCP) or non-HCP related office visits that have occurred since the previous study visit.
- Randomize the subject only if s/he meets all inclusion criteria and no exclusion criteria.
- Verify that the subject has fasted for at least 8 hours.
 - Record fasting status in the source and CRF
 - If the subject reports having eaten within 8 hours, document accordingly in the source and CRF and remind the subject that fasting is required prior to all study visits.
- Obtain urine sample for urinalysis.
- Perform a urine-based β -hCG pregnancy test in females of childbearing potential.
- Obtain blood samples for serum chemistry, hematology, and coagulation tests.
- Obtain blood samples for:
 - OCA, C4, and fibroblast growth factor-19 (FGF-19)
 - Markers of hepatic fibrosis and/or inflammation (including enhance liver fibrosis [ELF])

- Genetics (see [Section 11.1.2.3](#))
- Blood sample for future analysis (refer to Section 11.1.2.3)
- Access the IWRS and dispense investigational product
- Instruct the subject to begin dosing on the day after the Day 0 visit (ie, on Day 1). Instruct the subject to swallow the tablet whole; s/he must not chew, divide, or crush the tablet.
- Provide the subject with a dosing diary to document his or her dosing.
- Schedule the next visit, reiterate dosing instructions, and advise the subject:
 - NOT to take investigational product on the morning of the next visit, and
 - To bring the investigational product bottle(s); s/he will dose at the clinic (if this is in compliance with the established dosing frequency), and
 - To fast overnight (at least 8 hours) prior to the next visit. Fasting is required prior to all study visits, but water is permitted.

9.7.8. Month 1 Procedures:

- Assess and record AEs
- Review and record concomitant medications.
- Assess investigational product compliance, perform investigational product accountability, and review dosing diary with the subject.
- Obtain blood samples for serum chemistry, hematology, and coagulation tests.
- Provide the subject with a dosing diary to document his or her dosing.
- In the event it is not feasible for the subject to return to the site for the above referenced procedures, the following alternative visit procedures are available to help ensure compliance with the Month 1 visit requirements:

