13.1.3. Primary Efficacy Analysis

The primary efficacy endpoint will be the time to first occurrence of one of the following post-randomization:

- Death (all-cause)
- Liver transplant
- MELD score ≥ 15
- Hospitalization (as defined by a stay of 24 hours or greater) for new onset or recurrence of:
 - Variceal bleed
 - Encephalopathy (as defined by a West Haven score of ≥ 2)
 - Spontaneous bacterial peritonitis (confirmed by diagnostic paracentesis)
- Uncontrolled ascites (diuretic resistant ascites requiring therapeutic paracentesis at a frequency of at least twice in a month).
- Hepatocellular carcinoma confirmed by 2 complimentary imaging modalities.

The primary efficacy analysis will compare randomized OCA to randomized placebo with respect to the primary efficacy endpoint using the ITT population. Only adjudicated events will be included in analyses. The 2 treatment groups will be compared using the log rank test stratified by the randomization stratification factor. Kaplan-Meier (KM) estimates of the distribution of the time-to-event will be tabulated and graphed by treatment group. The tabulation will include the KM estimate of the medians and corresponding 95% confidence intervals (CIs), if the medians can be estimated. The number and percent of subjects censored and with events will be presented. The hazard ratio and 95% CI will be determined based on a Cox regression model stratified by randomization strata to estimate the magnitude of the effect.

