13.4. Adjudication Committees

All suspected liver-related clinical outcomes, MACE/Expanded MACE, and drug-related hepatic injury events that occur after administration of the first dose of investigational product will be reviewed by the following blinded adjudication committees, depending on event type, before inclusion in any analysis. The 3 committees and event types they are responsible for adjudicating are as follows:

- Cardiovascular Adjudication Committee (CAC): Adjudicates all suspected MACE, including all deaths
- Hepatic Outcomes Committee: Adjudicates all deaths and suspected liver-related outcomes
- Hepatic Safety Committee: Adjudicates all suspected drug-related hepatic injury events

Each adjudication committee will have a charter that documents the reporting of events by the study site, definition of the suspected events to be adjudicated, supply of source documentation to the committee, entire data flow and process from committee membership, review of the events by the committee, reporting of the final assessment, and the working procedures of the committee.

The adjudication committee members will include experts with relevant adjudication experience; they will not be involved in the study as Investigators, DMC members, or consultants. Any candidate found to have a conflict or whose name is listed on the FDA debarment list is not offered membership. Conflicts of interest are assessed regularly, and if members are found to have a new conflict of interest they will be replaced.

The adjudication of suspected events will be based on available source documentation, including but not limited to individual clinical study data, hospital records, histology, discharge summaries, and/or death certificates. The adjudication committees will not receive any individual subject treatment or site-specific information. The assessment of events will be conducted in compliance with study-specific procedures, manuals, good clinical practice (GCP), and all other applicable regulatory requirements, including the archiving of essential documents.

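### The population named Intent-to-Treat requires a dose, and section 13.4 starts adjudication at first dose, although the primary endpoint runs from randomization and the synopsis has every event adjudicated.

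*Protocol*

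**What the plan says.** All references are to the current protocol (Version 3).

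- **Populations (13.1.1).** "The Randomized Population will include all randomized subjects". The ITT Population is narrower: it "will include all randomized subjects who receive any amount of investigational product (OCA or placebo". Its role is explicit: "The ITT Population will be the primary population used for efficacy analyses". Subjects in it are grouped by randomized treatment.
- **Primary analysis (13.1.3).** OCA and placebo are compared "with respect to the primary efficacy endpoint using the ITT population". Section 13.1.4 uses the same set for the key secondary endpoints.
- **Time origin (13.1.3).** "The primary efficacy endpoint will be the time to first occurrence of one of the following post-randomization". Only adjudicated events enter the analysis.
- **Adjudication (13.4).** The committees review suspected events "that occur after administration of the first dose of investigational product", and this review precedes inclusion in any analysis.
- **Synopsis (Primary Efficacy Endpoint).** An independent committee adjudicates every event in enrolled subjects. There is no first-dose condition.
- **First dose (9.7.7; also 9.1 and 9.7.1).** "Instruct the subject to begin dosing on the day after the Day 0 visit".
- **No follow-up data (13.1.10.1).** A subject with no data after randomization is counted as an event on Day 1, which is described as the first dosing day.

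**The concern.** An intention-to-treat comparison keeps everyone who was randomized. Here, membership of the primary set depends on something that happens after randomization, away from the clinic. A result from this set would be reported as ITT although it is a modified ITT result, and section 13.1 specifies no all-randomized efficacy analysis beside it.

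The other rules do not fit together either. An event between randomization and a delayed first dose meets the endpoint definition in 13.1.3, is adjudicated according to the synopsis, and is not adjudicated according to 13.4. A subject with no data after randomization has no record of having dosed. Depending on what is presumed about dosing, that subject is either an imputed event or absent from the primary analysis.

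The protocol fixes the population, the time origin, the adjudication start and the imputation rule itself, so these are not details left for the SAP. This is a confirmatory outcomes trial with one hierarchical test sequence (13.1.11), so its primary set and event count should have a single reading.

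**Working it through.** **1. The plan's own figure.** Inputs from 13.1.2: hazard ratio 0.60, two-sided 5% level, 80% power, 1:1 allocation. Schoenfeld's formula gives

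events = 4 × (1.960 + 0.842)² / (ln 0.60)² = 120.3, rounded up to 121.

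Power at 121 events is 80.2%. The stated figure is reproduced.

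**2. Event probabilities under the plan's assumptions.** Placebo survival of 0.5 at 8 years gives a hazard of ln 2 / 8 = 0.0866 per year. The OCA hazard is 0.60 × 0.0866 = 0.0520. With uniform accrual over 2 years and 6 further years of follow-up, the probability of an event is

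1 − [exp(−6λ) − exp(−8λ)] / (2λ)

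This is 0.454 on placebo and 0.305 on OCA, with a mean of 0.379. Then 121 / 0.379 = 319 subjects without dropout, or 355 with 10% loss. The planned figure of about 350 is consistent with this.

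**3. Events in the gap before first dose.** The mean hazard is (0.0866 + 0.0520) / 2 = 0.0693 per year. Over one day in 350 subjects: 350 × 0.0693 / 365.25 = 0.07 events. If the gap were 14 days, the figure would be about 0.9.

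**4. Never-dosed subjects.** The protocol gives no rate, so the rates below are assumptions.

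| Never dosed | Subjects (of 350) | Events at trial-wide rate 121/350 | Events at placebo rate 0.454 |
|---|---|---|---|
| 1% | 3.5 | 1.2 | 1.6 |
| 2% | 7 | 2.4 | 3.2 |
| 3% | 10.5 | 3.6 | 4.8 |

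This gives about 4-11 subjects and roughly 1-5 events.

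**5. Effect of analysing all randomized subjects.** Suppose never-dosed OCA subjects have the placebo hazard. To a first approximation the all-randomized hazard ratio is f × 1 + (1 − f) × 0.60, where f is the never-dosed share. For f = 1%, 2% and 3% this is 0.604, 0.608 and 0.612. Power at 121 events is then about 79%, 78% and 77%.

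**6. What happens if 13.1.10.1 is left unchanged.** In an all-randomized analysis, each never-dosed subject with no later data would become a Day 1 event. At the assumed 1-3%, that is at most 4-11 imputed events, or 4/121 = 3% to 11/121 = 9% of the target. This would outweigh the problem being corrected, so the rule has to change together with the population.

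**The case against.** The strongest reply is that this is a labelling and wording matter with almost no numerical consequence. Much of that stands. The trial is double-blind, so failure to start treatment is unlikely to depend on arm. Section 9.3 has compliance confirmed by counts of returned tablets, so dosing status does not rest on self-report alone. Subjects who stop product are followed to the end of the study (7.4.2, 8.4.2, 13.1.10). One committee bullet in 13.4 covers all deaths, which may be broader than its lead-in sentence. Section 13.1.1 says in general terms that the listed populations will be used, and an all-randomized sensitivity analysis could appear in the SAP.

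A reader might infer three stronger things that the text does not support:

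- **That the arms are not compared as randomized.** Section 13.1.1 says that the ITT set is grouped by randomized treatment. The only departure is the omission of never-dosed subjects.
- **That events in never-dosed subjects are lost twice.** Such subjects are already outside the primary set, so the adjudication rule takes nothing further from that analysis. For dosed subjects it bites only between randomization and first dose.
- **That part of the 121 events is lost and power falls short.** The target is a count of adjudicated events and the study runs until they accrue. Events never sent to adjudication were never among the 121.

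The objection does not remove the conflict between 13.4 and the synopsis, the poor fit of 13.1.10.1, or the assignment of the primary analysis to a dosed-only set under the name ITT. The SAP could add an analysis, but the protocol has already fixed the primary one.

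**Conclusion.** The point holds as a defect of definition and consistency that should be corrected. The primary and key secondary efficacy analyses use a modified ITT set labelled ITT. The endpoint's time origin and the start of adjudication disagree, and section 13.4 contradicts the synopsis. The rule for subjects without data does not fit a set that requires dosing.

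The expected numerical effect is small: about 0.07 events in the planned one-day gap, and roughly 1-5 events in about 4-11 subjects if 1-3% never dose. The never-dosed rate is an assumption; the event counts also rest on the plan's own survival assumptions. The 121 events, the 80% power and the enrolment of about 350 are not called into question.

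**What to change.** 1. **13.1.1, 13.1.3, 13.1.4:** run the primary and key secondary efficacy analyses on all randomized subjects, as randomized. Keep the dosed set as a sensitivity analysis and name it modified ITT.
2. **13.4:** start adjudication of outcome events at randomization, in line with 13.1.3 and the synopsis.
3. **13.1.10.1:** censor subjects with no post-randomization data at randomization. Keep the Day 1 event imputation only as a sensitivity analysis.

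The three changes belong together: making the first without the third would bring in the imputed events shown in step 6 of the working. The cost is wording in these sections, follow-up of never-dosed subjects for outcomes, and a very slight dilution of the effect estimate (hazard ratio about 0.604-0.612 instead of 0.60 at 1-3% never dosed, with power of about 79-77% at 121 events).

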13.1.1.1. Comparability of Historical Controls

Utilization of both historical control/observational databases (UK-PBC and Global PBC Study Group), with more than 6000 subjects each, allow for a rigorous subject level meta-analysis. The historical databases include long-term follow up, detailed subject-level information such as

baseline clinical characteristics, longitudinal liver biochemistry, and long-term outcomes, and span a broad range of subject characteristics that may influence disease (disease state, age, gender, and regional differences in standard of care). Historical controls from both databases will be chosen based on the same study inclusion/exclusion criteria where possible.

13.1.2. Determination of Sample Size

The following assumptions were used in sample size calculations:

- Exponential survival curves, placebo survival estimate of 0.5 at 8 years with a hazard ratio of 0.60, and total study duration of 8 years, allowing for 2 years accrual and 6 years of follow up.
- Subjects will be randomized in a 1:1 ratio to placebo or OCA.
- The 2 groups will be compared using a 2-sided log rank test at the 5% level of significance.

Based on the randomization ratio, significance level, and assumed hazard ratio, a total of 121 events (both groups combined) will provide 80% power to demonstrate a statistically significant difference between OCA and placebo on time to liver-related outcomes, including all-cause mortality.

In addition, based on the remaining assumptions stated above, it is estimated that approximately 350 subjects will be enrolled to attain 121 events.

13.1.2.1. Sample Size Re-Estimation Plan

Conducting a long-term outcomes study given the low disease prevalence, relatively slow disease progression, and ethical considerations, which in combination will impact recruitment and event rates, is inherently difficult. As stated in ICH E9, in long-term trials there is an opportunity to check the assumptions that underlay the original design and sample size calculations. The power stated above depends on the total number of events. Thus, the overall survival function can be estimated without unblinding.

Therefore, starting approximately 2 years after the first subject is randomized, the aggregate event rate and sample size based on recruitment and retention will be evaluated in a blinded manner quarterly. This evaluation will determine if any increases in number of subjects are required in order to obtain a total of 121 adjudicated events for the final analysis in the combined groups. Specifically, the pooled number of events will be available during the study in a blinded manner, without any knowledge of the comparative efficacy in the treatment groups. This method for evaluating the sample size does not inflate the type I error rate. Additional subjects may be enrolled as appropriate.

If after 4 years of accruing subjects, despite increases in the number of subjects, it is determined that at least an additional 2 years (ie, total study duration of at least 10 years) are needed to randomize sufficient subjects to achieve a total of 121 adjudicated events, all subjects enrolled from that point forward will receive open-label OCA. Previously randomized subjects will continue to be treated in a blinded manner with either OCA or matching placebo. If this modification is implemented, the alternative primary efficacy analysis is specified in [Section 13.1.9](#).

Any revised sample size or changes to treatment allocation will be justified and documented in a protocol amendment and in the CSR.

13.1.3. Primary Efficacy Analysis

The primary efficacy endpoint will be the time to first occurrence of one of the following post-randomization:

- Death (all-cause)
- Liver transplant
- MELD score ≥ 15
- Hospitalization (as defined by a stay of 24 hours or greater) for new onset or recurrence of:
 - Variceal bleed
 - Encephalopathy (as defined by a West Haven score of ≥ 2)
 - Spontaneous bacterial peritonitis (confirmed by diagnostic paracentesis)
- Uncontrolled ascites (diuretic resistant ascites requiring therapeutic paracentesis at a frequency of at least twice in a month).
- Hepatocellular carcinoma confirmed by 2 complimentary imaging modalities.

The primary efficacy analysis will compare randomized OCA to randomized placebo with respect to the primary efficacy endpoint using the ITT population. Only adjudicated events will be included in analyses. The 2 treatment groups will be compared using the log rank test stratified by the randomization stratification factor. Kaplan-Meier (KM) estimates of the distribution of the time-to-event will be tabulated and graphed by treatment group. The tabulation will include the KM estimate of the medians and corresponding 95% confidence intervals (CIs), if the medians can be estimated. The number and percent of subjects censored and with events will be presented. The hazard ratio and 95% CI will be determined based on a Cox regression model stratified by randomization strata to estimate the magnitude of the effect.

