9.4. Randomization and Blinding

This study will be conducted in a double-blind, placebo-controlled manner. Allocation to one of two treatment groups (OCA or placebo) will occur on a 1:1 ratio across sites and will be stratified by UDCA treatment (yes/no) and mean baseline bilirubin categories ($>ULN/\leq ULN$), as specified by the central laboratory. The randomization will be based on a predefined randomization code (generated by the Sponsor or designee) using an interactive web response system (IWRS), which the Sponsor intends will serve as a computer-based subject registration system at Screening and Day 0. The IWRS will serve as an investigational product inventory and management system and may be integrated with the study database.

The Investigator or designee will be required to register the subject in the IWRS and may be prompted to provide subject data necessary to properly randomize and allocate the subject to treatment. A randomization number will be assigned (refer to [Section 9.5.2](#), below) and investigational product dispensing information (ie, bottle number[s]) will be provided.

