Hematology	Hemoglobin, hematocrit, white blood count with differential, neutrophils, lymphocytes, monocytes, eosinophils, basophils, platelets, red blood cell count (including MCV, MCH, MCHC)
Coagulation	Prothrombin time (PT), partial thromboplastin time (PTT), international normalized ratio (INR)
Urinalysis	pH, specific gravity, total protein, glucose, ketones, bilirubin, blood, microscopic exam, urobilinogen, albumin, creatine, leucocytes, nitrates, albumin/creatinine ratio (if positive)
Biomarkers of Hepatic Fibrosis and/or Inflammation	IgM, C-reactive protein (CRP), TNF- α , FGF-19, CK-18, ELF, and others as determined during course of study
Measurement of Liver Fibrosis	Fibroscan
Bone Density Assessment	DEXA
Genetics	DNA including single-nucleotide polymorphisms (SNPs) that may be involved in PBC; RNA
Blood Sample for Future Analysis	PBC autoantibodies and other cytokines and interleukins TBD
Other	OCA (parent and conjugates [glyco and tauro]) and C4

The Investigator should manage subjects with clinically significant lipoprotein abnormalities using local standard of care procedures as appropriate after assessing the individual subject's total cardiovascular risk profile.

Urine-based β -hCG pregnancy tests will be performed in female subjects of childbearing potential per protocol specified visits. If a urine pregnancy test is positive, a serum pregnancy test must be performed to confirm the result. If positive, the Sponsor must be notified and the subject will be followed, as outlined in [Section 12.1.9](#) through pregnancy outcome.

MELD scores, Child-Pugh score, and MRS will be calculated at screening, and at quarterly (MELD and Child-Pugh scores) or semi-annual (MRS) visits based on serum chemistry and coagulation.

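### Section 13.1.3 adjusts the primary comparison only for two binary factors and leaves continuous baseline prognostic values unused: efficiency forgone, not an invalid test

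*Protocol*

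**What the plan says.** Section 13.1.3 compares the arms with a log-rank test stratified by the randomization factor. For the effect size, "The hazard ratio and 95% CI will be determined based on a Cox regression model stratified by randomization strata". No further covariate is named for either. Section 9.4 defines the allocation as "stratified by UDCA treatment (yes/no) and mean baseline bilirubin categories", the bilirubin categories being above or not above ULN.

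Section 12.2.7 states that "MELD scores, Child-Pugh score, and MRS will be calculated at screening". Section 9.7.5 builds the Mayo Risk Score from bilirubin, albumin, prothrombin time, peripheral edema and diuretic use. Table 1 and Section 9.7.6 place its assessment at Screening Visit 1. The only analysis of the score in the protocol is as a change outcome in Section 13.1.5.

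By contrast, the ANCOVAs for ALP and total bilirubin in Section 13.1.4 adjust for the continuous baseline value as well as the stratification factor.

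**The concern.** The bilirubin factor pools every value from just above ULN to the eligibility ceiling of 3 times ULN (Section 8.2) into one category. Albumin and prothrombin time are not used at all. There is an internal reason to expect baseline liver function to be prognostic: Section 8.3 admits subjects with MELD up to 12, and MELD of 15 or more is itself a primary event, so the baseline value sets the distance to an endpoint.

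The trial is designed at 80% power with 121 events, and Section 13.1.2.1 describes recruitment and event accrual as difficult. Under Section 13.1.11 a non-significant primary result makes all key secondary tests exploratory. Power available from data already collected, with no extra patient, is therefore worth having. The protocol itself fixes the primary model, so the point does not depend on what the SAP may add.

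**Working it through.** **Inputs from Section 13.1.2.** The arms are "compared using a 2-sided log rank test at the 5% level of significance"; "Subjects will be randomized in a 1:1 ratio to placebo or OCA"; "placebo survival estimate of 0.5 at 8 years with a hazard ratio of 0.60"; "allowing for 2 years accrual and 6 years of follow up"; about 350 subjects.

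**Reproducing the plan's figure.** The Schoenfeld formula for 1:1 allocation is D = 4(z₀.₉₇₅ + z₀.₈₀)² / (ln HR)².

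- D = 4 × (1.960 + 0.842)² / (ln 0.60)² = 4 × 7.85 / 0.261 ≈ 120.3, rounded up to 121.
- Power at 121 events = Φ(√121/2 × 0.511 − 1.960) = Φ(0.85) = 80.2%.

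This agrees with "a total of 121 events (both groups combined) will provide 80% power".

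**What is assumed.** The score's prognostic strength within strata is not in the documents. It was varied in two simulations. Both used 350 subjects, 2-year accrual, analysis at the 121st event and placebo event-free probability 0.5 at 8 years.

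*Simulation A* (four strata, 1,500 trials per setting; conditional HRs chosen so that the unadjusted HR was about 0.57 to 0.60). The planned stratified log-rank test is compared with stratified Cox plus continuous score:

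| HR per SD of score | Planned power | Cox plus score | Gain (points) |
|---|---|---|---|
| 1.3 | 79% | 80% | 1 |
| 1.5 | 79% | 82% | 3 |
| 2.0 | 81–83% | 87–90% | 6–7 |
| 2.5 | 83–85% | 92–94% | 9 |

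The Monte Carlo standard error of each power figure is about √(0.8 × 0.2/1,500) = 1 point, so the smallest gain is close to noise. Log bilirubin alone gained only 0 to 2 points.

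*Simulation B* (3,000 trials per setting; two strata split 80/20 with a log-hazard gap of 0.5, also assumed). The score-conditional HR was set so that the HR within strata but averaged over the score is about 0.60, the reading under which the plan has its stated power:

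| SD of log hazard (HR per SD) | Planned → Cox plus score | SE of log HR, planned / with score | Planned → covariate-adjusted log-rank | CI narrower by (adjusted log-rank) |
|---|---|---|---|---|
| 0.5 (1.65) | 81.0 → 85.1% | 0.187 / 0.187 | 80.1 → 82.3% | 4% |
| 0.75 (2.12) | 81.1 → 88.6% | 0.187 / 0.188 | 79.8 → 85.7% | 8% |
| 1.0 (2.72) | 80.2 → 92.4% | 0.187 / 0.189 | 79.8 → 89.1% | 12% |
| 1.25 (3.49) | 79.5 → 95.8% | 0.187 / 0.190 | 79.9 → 91.5% | 16% |

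HR per SD is exp(SD). The last column is 1 − √(variance ratio), with ratios 0.919, 0.845, 0.770 and 0.703.

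**Two checks in simulation B.**

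- *Worthless score (SD 0):* power is 78.7% planned and 78.5% adjusted, so nothing is lost.
- *No treatment effect, SD 1.0:* one-sided error was 2.6% (stratified Cox), 3.1% (Cox plus score), 3.0% (stratified log-rank) and 2.7% (covariate-adjusted log-rank). The Monte Carlo standard error is √(0.025 × 0.975/3,000) ≈ 0.3 point, so there is no material inflation from adjustment.

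**Where the gain comes from.** In the Cox model the standard error of the log HR does not fall. The gain is that the score-conditional HR lies further from 1 than the HR averaged over the score. The interval narrows only with the covariate-adjusted log-rank approach, which leaves the target effect unchanged and reduces its variance.

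**The case against.** The strongest reply is that nothing here is wrong. Section 13.1.2 powers the trial on a log-rank test, Section 13.1.3 uses that test stratified by the factors used to randomize, and the event count reproduces. Choosing an adjusted test is then a preference, and an adjusted sensitivity analysis could sit in the SAP. The first part stands in full: the plan is valid and adequately powered for its stated effect. It does not remove the point, because the protocol fixes the primary model and a prespecified adjustment costs almost nothing when the score turns out to be uninformative.

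Four stronger readings are tempting, and the documents do not support them.

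- *The trial is underpowered as planned.* If 0.60 were the HR conditional on the score, simulation B would give the planned analysis only 74, 69, 62 and 54% power at SD 0.5, 0.75, 1.0 and 1.25. Section 13.1.2 attaches 0.60 to the log-rank comparison and does not condition it on any score. The shift of the unadjusted HR toward 1 is non-collapsibility, not bias.
- *Adding the score to the Cox model narrows the interval.* It does not, as the standard errors show.
- *Most subjects fall in one bilirubin stratum.* No split is given, and entry is by bilirubin and/or ALP above 5 times ULN.
- *Every subject has a screening Mayo Risk Score.* The screening calculation is in the current text of Section 12.2.7. The superseded text of that section in the same file has the score only at semi-annual visits, and Appendix D shows the Day 0 edema assessment was added by Amendment 1, when sites were already using the original protocol. Some early subjects may lack the edema component.

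It is also fair that eligibility narrows the score's range (bilirubin above 3 times ULN, MELD above 12 and complicated cirrhosis are excluded) and that bilirubin is already partly stratified. Both argue for taking the lower end of the range seriously.

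**Conclusion.** The point holds as a recommendation on efficiency. Section 13.1.3 leaves continuous prognostic values, obtained before randomization, out of the primary analysis. The planned test is valid and keeps its 80% power at 121 events.

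On assumed prognostic strength, adjustment adds about 1 to 3 power points at HR 1.3 to 1.5 per SD and about 6 to 9 or more at HR 2.0 to 2.5. It costs nothing in power if the score is uninformative and does not materially inflate type I error. A covariate-adjusted log-rank test would also narrow the interval by about 4 to 16% at log-hazard SD 0.5 to 1.25. These sizes rest on the assumed within-strata strength, the assumed stratum structure and a correctly specified linear score effect. The direction does not depend on the exact values.

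**What to change.** Before unblinding, amend Section 13.1.3 as follows:

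- Keep the randomization strata.
- Name one baseline covariate set: the continuous Mayo Risk Score, or log bilirubin, albumin and INR if edema data are missing for early subjects. State the missing-value rule.
- Choose one use of it. Either a covariate-adjusted stratified log-rank test, which keeps the marginal effect and narrows its interval, or the stratified Cox model with the covariate, which gains power but reports a conditional HR.
- State whether the reported HR is conditional or marginal, so that test and estimate address the same effect.
- Retain the unadjusted stratified log-rank test as sensitivity analysis.
- Apply the same model to time to liver transplant or death, which inherits the primary methodology through Section 13.1.4.

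The cost is protocol and SAP wording: no patient, visit or sample is added. The downsides are small but real. The amendment alters step 1 of the testing sequence in an ongoing trial, so it must be dated and justified while the data are blinded. The covariate and its functional form must be fixed in advance, and under the Cox option readers must be told that the HR is conditional on baseline risk.
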